### Incomplete Death Date

Identify date of last known alive (LA) prior to death from the following:

1. Date of decision to discontinue study treatment from End of Treatment CRF
2. Date of last radiographic assessment from End of Radiographic Follow Up CRF
3. Date last known alive from Survival Follow Up CRF
4. Date of last lab assessment from the Labs dataset

If *year* is missing (or completely missing): set to date of LA + 1

If only *day* is missing: set to the maximum of the first of month or LA + 1

If *month* and *day* are missing:

If *year* of LA = *year* of death

Set death date to date of LA + 1

If *year* of most-recent contact < *year* of death

Set *month* and *day* to Jan 1st.

### Incomplete Study Treatment Start Date

Define previous sequential dosing “milestone” as the latest of previous dose stop date, previous dose hold stop date, date of first dose or randomization date.

If *year* is missing (or completely missing): set to date of previous sequential dosing “milestone” + 1

If (*year* is present and *month* and *day* are missing) or (*year* and *day* are present and *month* is missing): set to January 1st

If *year* and *month* are present and *day* is missing: set to the first day of the month

If the imputed date is before the previous sequential dosing “milestone”: set to the date of previous sequential dosing “milestone” + 1

### Incomplete Study Treatment Stop Date

Define next sequential dosing “milestone” as the earliest of next dose start date, next dose hold start date, date of last dose from EOT CRF or the cutoff date.

If *year* is missing (or completely missing): set to date of next sequential dosing “milestone” - 1

If (*year* is present and *month* and *day* are missing) or (*year* and *day* are present and *month* is missing): set to December 31st

If *year* and *month* are present and *day* is missing: set to the last day of the month

If the imputed date is after the next sequential dosing “milestone”: set to the date of next sequential dosing “milestone” - 1

## **Appendix B: Rounding Rules for Reported Percentages**

For percentages  $\geq 10\%$ :

- Values  $\geq X.5$  or above round to  $X+1$ .
- Values  $> X$  but  $< X.5$  round to  $X$ .

For percentages  $< 10\%$ :

- Values  $\geq X.Y5$  or above round to  $X.Y+0.1$ .
- Values  $> X.Y$  but  $< X.Y5$  round to  $X.Y$ .

## **Appendix C: Imputation Rules for Laboratory Values Outside of Quantification Range**

- Lab values below the lower level of quantification (LLQ) that are reported as “< LLQ” or “≤ LLQ” in the database will be imputed by  $LLQ \times 0.99$  for analysis purposes. However, the original value will also be maintained.
- Lab values above the upper level of quantification (ULQ) that are reported as “> ULQ” or “≥ ULQ” in the database will be imputed by  $ULQ \times 1.01$  for analysis purposes. However, the original value will also be maintained.

## Appendix D: EQ-5D-5L Index Value Conversion Guidelines

The EQ-index conversion algorithm (EQ-5D-5L User Guide 2.1, April 2015. Available from: <http://www.euroqol.org/about-eq-5d/publications/user-guide.html>):

- Calculate **health state**
  - Each of the 5 dimensions comprising the EQ-5D descriptive system is divided into 5 levels of perceived problems:
    - Level 1: indicating no problem
    - Level 2: indicating slight problems
    - Level 3: indicating moderate problems
    - Level 4: indicating severe problems
    - Level 5: indicating extreme problems
  - A unique health state is defined by combining 1 level from each of the 5 dimensions.  
For example, state 11111 indicates no problems on any of the 5 dimensions, while state 12345 indicates no problems with mobility, slight problems with washing or dressing, moderate problems with doing usual activities, severe pain or discomfort and extreme anxiety or depression. Note that missing values will be coded as '9'. Ambiguous values will be treated as missing values.
- **EQ-index values** for each country = **health state \* the country specific conversion factors** for each dimension (EQ-5D-5L Index Value Calculator, version 1)

## Appendix E: Estimands Terminology

Source: ICH E9 R1

### Estimand Attributes:

#	Estimand Attribute
1	The population, that is, the patients targeted by the scientific question.
2	The variable (or endpoint), to be obtained for each patient, that is required to address the scientific question.
3	The specification of how to account for intercurrent events to reflect the scientific question of interest.
4	The population-level summary for the variable which provides, as required, a basis for a comparison between treatment conditions.

### Strategies for Addressing Intercurrent Event(s):

Strategy	Description
Treatment policy	The occurrence of the intercurrent event is irrelevant: the value for the variable of interest is used regardless of whether or not the intercurrent event occurs.
Composite	The occurrence of the intercurrent event is taken to be a component of the variable, i.e. the intercurrent event is integrated with one or more other measures of clinical outcome as the variable of interest.
Hypothetical	A scenario is envisaged in which the intercurrent event would not occur: the value to reflect that scientific question of interest is that which the variable would have taken in the hypothetical scenario defined.
Principal stratum	The target population might be taken to be the principal stratum (see Glossary) in which an intercurrent event would not occur.
While on treatment	Response to treatment prior to the occurrence of the intercurrent event is of interest.

## Appendix F: Performance Scales: Karnofsky and ECOG Grades

Karnofsky Status	Karnofsky Grade	ECOG Grade	ECOG Status
Normal, no complaints	100	0	Fully active, able to carry on all pre-disease performance without restriction
Able to carry on normal activities. Minor signs or symptoms of disease	90	0	Restricted in physically strenuous activity but ambulatory and able to carry out work of a light or sedentary nature, e.g., light housework, office work
Normal activity with effort	80	1	Restricted in physically strenuous activity but ambulatory and able to carry out work of a light or sedentary nature, e.g., light housework, office work
Care for self. Unable to carry on normal activity or to do active work	70	1	Ambulatory and capable of all selfcare but unable to carry out any work activities. Up and about more than 50% of waking hours
Requires occasional assistance, but able to care for most of his needs	60	2	Ambulatory and capable of all selfcare but unable to carry out any work activities. Up and about more than 50% of waking hours
Requires considerable assistance and frequent medical care	50	2	Capable of only limited selfcare, confined to bed or chair more than 50% of waking hours
Disabled. Requires special care and assistance	40	3	Capable of only limited selfcare, confined to bed or chair more than 50% of waking hours
Severely disabled. Hospitalization indicated though death non-imminent	30	3	Completely disabled. Cannot carry on any selfcare. Totally confined to bed or chair
Very sick. Hospitalization necessary. Active supportive treatment necessary	20	4	Completely disabled. Cannot carry on any selfcare. Totally confined to bed or chair
Moribund	10	4	Completely disabled. Cannot carry on any selfcare. Totally confined to bed or chair
Dead	0	5	Dead

## Appendix G: Time to Onset (TTO) Algorithm

1. Analysis unit: episode
2. Analysis method: KM
3. Analysis population: subgroup of those with the specified PT in a Grouped AE term
4. For time to onset for Grouped AEs of any grade
  - a. For each subject identify all records with PTs that are members of the Group
  - b. Sort records by subject, Group and AE start date
  - c. For each subject select the first PT within each grouping
  - d.  $Aval = (AE\ start\ date - treatment\ start\ date + 1) / 30.4375$
  - e. Consider this as an event (CNSR=0)
  - f. Subjects who do not have any events for a grouping are considered censored and their  $Aval = (\text{end of observation period date} - treatment\ start\ date + 1) / 30.4375$
5. For time to onset of Grouped AEs of grade 3-5 follows above steps (a) to (f) except (a) is modified to include only AEs of grade 3 to 5

## Appendix H: Time to Resolution (TTR) Algorithm

1. Analysis unit: episode
2. Analysis method: KM
3. Analysis population: subgroup of those with the specified PT or Grouped AE term
4. For specific AE preferred terms (PT):
  - a. Exelixis AE CRF is one-episode-per page and captures all changes in event characteristics (grade, seriousness, relationship) as “rows” within the same record.
  - b. An “episode” is thus defined as:
    - i. Start = earliest interval start date within the record
      1. For “Grade 3-5” summaries, start = earliest interval start date within the record where Grade  $\geq 3$
    - ii. Stop = stop date value for the last interval within the record
      1. If missing or event ongoing:
        - a. Set to end date of safety observation period
        - b. Set status to ‘censored’
      2. If not missing
        - a. If grade  $\geq 5$  set status to ‘event’
        - b. If grade  $< 5$  then set status to ‘censored’
  - c. Compute TTR per Kaplan-Meier (KM) analysis for each PT episode
    - i. May include  $> 1$  episode per subject (with same or different verbatim term) with same PT
5. For grouped AEs: Option 1
  - a. Identify all records with PTs that are members of the Group; assign each the Grouped AE name.
  - b. Compute episode start/stop/status for each PT as above
  - c. Consolidate contiguous (overlapping, bookended, or 1-day gap) records into a common episode [easier said than done]
    1. For “Grade 3-5” summaries, start = earliest interval start date within the record where Grade  $\geq 3$ ; after consolidation
  - d. Compute TTR per KM for each Grouped AE value episode
    - i. May include  $> 1$  episode per subject (with same or different PT) with same Grouped AE name

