**Table H-2: Requirements for Following up on Events Documented and Reported in Table H-1:**

Event type	If ongoing at...	...follow until...	Event follow-up requirements		
			...and document following on:		
			Source documents	EDC CRF	Drug Safety SAE Form
AE: nonserious, non-AESI	FU-1	NA	status at FU-1	status at FU-1	NA
SAE: not related, non-AESI	FU-2	NA	status at FU-2	status at FU-2	status at FU-2
Related AE leading to study treatment discontinuation	FU-2	Resolution b	evidence of resolution	status at FU-2	NA (if nonserious)
AESI: regardless of seriousness (AESIs: irAEs, potential DILI, Other; Table 8-1 )	FU-2	Resolution b	evidence of resolution	status at FU-2	evidence of resolution
Related SAE	FU-2	Resolution b	evidence of resolution	status at FU-2	evidence of resolution

AE, adverse event; AESI, adverse event of special interest ([Table 8-1](#)); EDC, electronic CRF data capture system; CRF, case report form; DILI, drug-induced liver injury; EOT date, end of treatment date (later of the date of decision to discontinue study treatment or date of last dose); FU-1, follow-up visit 30 days after EOT date; FU-2, follow-up visit 100 days after EOT date; IC, informed consent; irAE, immune-related AE; NA, not applicable; SAE, serious AE.

a See CRF completion guidelines for instructions regarding the appropriate page(s) to be completed

b Defined as: AE is fully resolved or  $\leq$  Grade 2 severity or the event is deemed stable/irreversible by the Investigator

CONFIDENTIAL

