## **8.1. Adverse Events**

Adverse event terms recorded on the CRF will be mapped to preferred terms and system organ class using the MedDRA. The severity of AEs will be measured by CTCAE version 5.0 (Common Terminology Criteria for Adverse Events [CTCAE] Version 5.0 2009). The Investigator will judge each event to be “not related” or “related” to each study treatment component. Adverse events related to study treatment summaries will include all events that are judged to be related to at least one treatment component in the respective study arms.

A TEAE is defined as any event with an onset date on or after the date of the first dose of study drug or any ongoing event on the date of the first dose of study drug that worsens in severity after the date of the first dose of study drug.

Unless otherwise specified, only TEAEs with an onset date (or date of increase in severity) through the end of the relevant safety observation period (see [Section 4.5](#)) will be tabulated in summary tables.

All deaths starting at any time after informed consent, irrespective of when they occur, are recorded in the CRFs as Grade 5 AEs. However, only those associated with an event starting after informed consent through 100 days after the date of the decision to discontinue the last component study treatment (or starting at any time after informed consent and judged to be related to study treatment) require reporting them as an SAE.

For the purpose of calculating treatment emergence and inclusion in summary tables, incomplete onset dates will be imputed as detailed in [Appendix A](#).

An overall summary of adverse events will be provided with the number and percent of subjects who experienced the following types of events during the standard safety observation period

(unless otherwise noted as “at any time” or “during the extended safety observation periods” below) in each study treatment arm. Unless specified explicitly otherwise, the related criteria will be with respect to the study treatment regimen (at least one treatment component in the treatment regimen meeting the criteria) for the below summaries:

- Subjects with a TEAE
- Subjects with a Related TEAE
- Subjects with a Serious TEAE
- Subjects with a Serious Related TEAE
- Subjects with a Worst-Grade 3 or 4 TEAE
- Subjects with a Worst-Grade 3 or 4 Related TEAE
- Subjects with a Worst-Grade 3 TEAE
- Subjects with a Worst-Grade 3 Related TEAE
- Subjects with a Worst-Grade 4 TEAE

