TEAE included	Row-levels (sorted by)	Columns
AESIs leading to initiation of high-dose corticosteroids	Time to first onset of AESIs by Group Term	Any Grade, Grade 3-5
Time to Resolution		
AESIs	Time to Resolution by Group Term	Any Grade, Grade 3-5
AESIs leading to initiation of immune-modulating medication (choose the interval for the longest PT)	Time to Resolution by Group Term	Any Grade, Grade 3-5
AESIs leading to initiation of high-dose corticosteroids (choose the interval for the longest select PT)	Time to Resolution of AESIs by Group Term	Any Grade, Grade 3-5
Recur-after-Rechallenge		
AESIs	Group Term	Any Grade, Grade 3-5
AESIs leading to initiation of immune-modulating medication	Group Term	Any Grade, Grade 3-5
AESIs leading to initiation of high-dose corticosteroids	Group Term	Any Grade, Grade 3-5
Liver test abnormalities (laboratory data) ALT or AST > 3 x ULN ALT or AST > 10 x ULN		

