#### 8.4. Time-to Onset for Adverse Events of Special Interest

Time to onset of AESI PTs grouped in special categories since start of the study treatment will be summarized for events observed amongst subjects who experienced at least one AESI.

Descriptive statistics will be presented by any grade and grade 3-5 for each treatment arm for summaries shown in [Table 15](#). See algorithm details in [Appendix G](#).

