#### 8.5. Time-to Resolution of Adverse Events of Special Interest

Time to resolution for AESIs will be summarized by any grade and grade 3-5 by treatment arms for summaries shown in [Table 15](#) amongst subjects who experienced at least one AESI.

Analysis of time-to resolution will be by Kaplan-Meier method as described in [Section 7.1.5](#).

Number, percentage, median and 95% CI of the select PTs will be reported. See algorithm details in [Appendix H](#).

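### SAP Appendix H has the status labels for AESI time to resolution the wrong way round: resolved episodes are censored and fatal ones count as resolutions

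*SAP*

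**What the plan says.** SAP Section 8.5 plans a Kaplan-Meier analysis of time to resolution among subjects with at least one AESI, by any grade and by Grade 3-5. It sends the reader to Appendix H for the algorithm and promises that "Number, percentage, median and 95% CI of the select PTs will be reported". The rows themselves are in Table 16 ("Time to Resolution by Group Term"): all AESIs, those leading to immune-modulating medication, and those leading to high-dose corticosteroids.

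Appendix H step 4.b.ii takes the stop date of the last interval in the record as the end of the episode and then assigns a status:

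- Stop date missing or event ongoing (4.b.ii.1): censored at the end of the safety observation period.
- Stop date present and grade 5 or above (4.b.ii.2.a): "set status to ‘event".
- Stop date present and grade below 5 (4.b.ii.2.b): "then set status to ‘censored".

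For the grouped terms, step 5.b says "Compute episode start/stop/status for each PT as above", so the same status rule feeds the rows that will be reported. On the meaning of the grade, SAP Section 8.1 states that deaths "are recorded in the CRFs as Grade 5 AEs".

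**The concern.** In a time-to-resolution analysis the event is resolution. The written rule gives event status only to episodes that ended in death and censors every episode that ended in recovery. The resulting curve describes time to a fatal outcome under a resolution label.

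At stake are the number, percentage, median and confidence interval that Section 8.5 promises for each AESI group. How long immune-related toxicity lasts on the triplet compared with the doublet is useful safety information, and safety including immune-related events is a listed endpoint. Followed to the letter, the algorithm would leave most of these cells empty.

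The step also does not say which grade is tested, although step 4.a allows one record to hold several.

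**Working it through.** **Can the text be read another way?**

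1. *Reversed coding convention.* Appendix G, the companion algorithm for time to onset, treats occurrence of the named outcome as the event (CNSR=0). Appendix H itself uses the censored label in the ordinary sense for ongoing episodes, immediately above the two lines in question.
2. *Choice of grade row.* A record that was never fatal contains no Grade 5 row, so it is censored whichever row is tested.
3. *Overridden elsewhere.* Section 8.5 names the method and defers to Appendix H. Neither document contains another status rule.

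So, as written, the number of events equals the number of fatal episodes with a stop date. With no fatal episode it is 0 for any number of episodes, and S(t) = 1.0 throughout. This needs no assumption about the data.

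**Illustration.** The documents contain no resolution data, so the episode times below are assumed. There are ten episodes ending at weeks 1 to 10, and S is multiplied by (1 − 1/number at risk) at each event. *Corrected* means a non-fatal stop is an event, and fatal or ongoing episodes are censored.

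| Example | As written | Corrected |
|---|---|---|
| A: 9 resolved; week 10 ongoing | 0 events, S = 1.0, no median | 9 events, S(5) = 5/10 = 0.5, median 5 weeks |
| B: 8 resolved; week 3 fatal; week 10 ongoing | 1 event, 8 at risk, S = 7/8 = 0.875, no median | 8 events, median 6 weeks |
| C: 8 resolved; week 9 ongoing; week 10 fatal | 1 event, 1 at risk, S(10) = 0, median 10 weeks | 8 events, S(5) = 0.5, median 5 weeks |

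For B corrected: S(2) = 8/10 = 0.8. After the week 3 censoring, S(4) = 0.8 × 6/7 = 0.686, S(5) = 0.686 × 5/6 = 0.571 and S(6) = 0.571 × 4/5 = 0.457, the first value at or below 0.5.

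In A and C the corrected curve sits at exactly 0.5 between weeks 5 and 6, so a midpoint convention would report 5.5 weeks. The 10-week median in C as written is the time of the death.

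**Larger sets.** Sets of 1,000 episodes were simulated under these assumptions: exponential resolution times with median 1.5 months, exponential times to death with median 1.0 month, ongoing episodes censored uniformly over 1 to 12 months, 0 to 10% fatal, and 15% or 40% ongoing.

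| | Events | Result |
|---|---|---|
| As written | 0 to 100 | curve ends at 0.78 to 1.00; median never reached |
| Labels exchanged | 580 to 850 | median 1.9 to 3.7 months |

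**The case against.** The strongest reply is that this is a drafting slip with an obvious intention. The appendix title, Section 8.5 and Table 16 all name resolution, and the appendix still carries unfinished drafting notes. The output is descriptive, no formal safety comparison is planned, and the failure would usually be a table full of non-estimable medians, which a dry run would catch. That is fair as to consequence and sets the priority. It does not make the written rule correct, and a pre-specified algorithm should not depend on a programmer silently departing from it.

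A second point is that a misleading median is an edge case. Example C produces one only because the death comes last with one episode at risk; example B contains a death and yields no median. This stands. It also stands that a fatal episode recorded without a stop date would go to the missing/ongoing branch and be censored. The CRF instructions that would settle this are not in the documents.

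Third, the deciding grade can be inferred: the test sits under the definition based on the last interval. That is the natural reading, and one clause would make it explicit.

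Finally, exchanging the labels does not complete the specification. The reported rows are by group term, and step 5.c merges contiguous records without saying which status the merged episode takes. Table 16 adds a choice of the longest preferred-term interval that is not tied to that step. Death could also be handled as a competing event. These points are sound and add to the fix.

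**Conclusion.** The two labels in step 4.b.ii.2 are reversed; the missing/ongoing branch above them is right. Followed exactly, the rule yields no resolutions and no estimable median in any AESI group without a fatal episode. That conclusion rests only on the text and on Grade 5 meaning death. In groups with deaths the curve tracks time to death, but the usual symptom is still a median that is not reached. The size of the distortion in the illustrations depends on assumed episode times.

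The effect is confined to the three descriptive time-to-resolution rows of Table 16, each shown for any grade and Grade 3-5. It should be fixed before the safety tables are produced, and it does not threaten the trial's efficacy conclusions.

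**What to change.** In SAP Appendix H:

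- **Step 4.b.ii.2.** If a stop date is present and the last interval is not Grade 5, set the status to event. If the last interval is Grade 5, censor at the date of death. Leave 4.b.ii.1 as it is. If the sponsor prefers to treat death as a competing event, say so and name the estimator; either choice removes the reversal.
- **Definition.** State that the CRF stop date is taken as the resolution date. Protocol Table H-2 uses a wider meaning for follow-up, which includes improvement to Grade 2 or lower and cases where "the event is deemed stable/irreversible by the Investigator". One sentence prevents the two from being confused.
- **Step 5.c.** State which status a merged episode takes when its component records differ, and reconcile the step with the longest-interval note in Table 16.

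Two editorial corrections can go in at the same time. Section 8.5 cites Table 15, but the rows are in Table 16. For onset, Section 8.4 says "Descriptive statistics will be presented by any grade and grade 3-5 for each treatment arm" among subjects with at least one AESI, while Appendix G specifies Kaplan-Meier among subjects with the specified preferred term; the two should be reconciled.

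The cost is two corrected lines, a few clarifying sentences and one cross-reference, with no change to data collection. SAP Section 4.8 allows minor corrections by addendum approved before the final analyses; if the sponsor regards the change as substantive, the same section calls for a revised SAP.

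### Time to resolution of AESIs pools repeat episodes per subject under an ordinary 95% interval, and two Table 16 rows add an undefined selection rule

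*SAP*

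**What the plan says.** SAP Appendix H fixes the unit in its first line, "Analysis unit: episode", and names Kaplan-Meier as the method. For preferred terms the instruction is "Compute TTR per Kaplan-Meier (KM) analysis for each PT episode", and step 4.c.i allows more than one "episode per subject (with same or different verbatim term) with same PT". For grouped terms, step 5.d.i likewise allows more than one "episode per subject (with same or different PT) with same Grouped AE name".

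The only merging is in step 5.c and applies to grouped terms: "Consolidate contiguous (overlapping, bookended, or 1-day gap) records into a common episode". A recurrence after a longer gap stays a separate record. At preferred-term level nothing is merged.

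SAP Section 8.5 takes its Kaplan-Meier method from Section 7.1.5 and adds: "Number, percentage, median and 95% CI of the select PTs will be reported". Section 7.1.5 is the PFS analysis, where each subject contributes one record. Neither section nor Appendix H names a clustered, robust or bootstrap variance.

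Table 16 has three time-to-resolution rows:
- All AESIs: no selection rule.
- AESIs leading to immune-modulating medication: "choose the interval for the longest PT".
- AESIs leading to high-dose corticosteroids: the same note, with the word select before PT.

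Appendix H has no step that matches these notes.

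**The concern.** The usual Kaplan-Meier variance treats every record as independent. Two episodes of the same toxicity in one subject share that subject's biology, management and reporting habits, so some positive correlation is plausible. If it exists, the printed intervals claim more precision than the data carry.

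The Table 16 notes are a second problem. Appendix H keeps every episode, whereas two rows ask for a selection that it does not describe. Two programmers could produce different tables from the same data, and a pooled median does not estimate the same quantity as a median of selected long intervals.

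At stake is the description of how long immune-related toxicities last, which clinicians will read from these rows. No test or decision depends on it.

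**Working it through.** The plan states no interval width, precision target or event count for time to resolution, so there is no figure to reproduce. The inputs below that are not in the documents are assumptions.

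**Inputs**
- From the SAP: episode as unit, several per subject allowed, Kaplan-Meier median with 95% CI (Appendix H, Section 8.5).
- Assumed: mean episodes per affected subject *m* = 1.2, 1.5, 2; within-subject correlation *ρ* = 0, 0.3, 0.5.

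**Step 1. Design effect.** DE = 1 + (*m* − 1)*ρ*. The correct interval is √DE times the naive one. A nominal 95% interval covers 2Φ(1.96/√DE) − 1.

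| *m* | *ρ* | DE | √DE | coverage |
|---|---|---|---|---|
| any | 0 | 1.00 | 1.00 | 95.0% |
| 1.2 | 0.3 | 1.06 | 1.03 | 94.3% |
| 1.2 | 0.5 | 1.10 | 1.05 | 93.8% |
| 1.5 | 0.3 | 1.15 | 1.07 | 93.2% |
| 1.5 | 0.5 | 1.25 | 1.12 | 92.0% |
| 2.0 | 0.3 | 1.30 | 1.14 | 91.4% |
| 2.0 | 0.5 | 1.50 | 1.22 | 89.0% |

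For example, at *m* = 2 and *ρ* = 0.5, DE = 1 + 1 × 0.5 = 1.5 and √1.5 = 1.22.

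**Step 2. Simulation.** Each setting had 2,000 runs of 60 subjects with lognormal resolution times (true median 2.0), independent exponential censoring, and a Kaplan-Meier median with a log-log 95% CI. The number of episodes did not depend on their length. With 2,000 runs the Monte Carlo standard error at 95% is √(0.95 × 0.05/2000), about 0.5 percentage points.

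| mean episodes | pooled coverage, *ρ* = 0 / 0.3 / 0.5 | median if longest episode is taken, *ρ* = 0 / 0.3 / 0.5 |
|---|---|---|
| 1.2 | 94.7 / 94.7 / 95.2% | 2.22 / 2.18 / 2.16 |
| 1.5 | 95.4 / 93.0 / 91.9% | 2.56 / 2.43 / 2.36 |
| 2.0 | 96.3 / 92.0 / 89.5% | 3.01 / 2.80 / 2.66 |

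Using only the first episode per subject gave 94.7% to 95.7% in every setting. At 1.5 and 2 episodes the simulation agrees with the formula. At 1.2 episodes it shows no detectable loss up to *ρ* = 0.5.

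**Step 3. Effect of choosing the longest.** In these settings the pooled median stays at about 2.0. Taking each subject's longest episode raises it to between 2.16 (2.16/2.0, 8% up) and 3.01 (about 50% up). The choice of rule can therefore move the estimate noticeably.

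**Step 4. Comparison within the SAP.** Appendix G, on time to onset, also names the episode as its unit, but step 4.c keeps only the first qualifying term per subject within each grouping. The SAP resolves the multiplicity for onset and leaves it open for resolution.

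**The case against.** The episode unit is declared openly, so a median that describes episodes is the stated target. Appendix H also limits repeats: the CRF holds one episode per page with grade changes kept inside the record (step 4.a), and near-contiguous records are merged for grouped terms (step 5.c). The mean number of episodes may be close to 1, where little is lost. SAP Section 8 plans no formal comparison of the arms on safety. All of this stands. It limits the size of the point but does not supply a valid interval when repeats and correlation are present.

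Three stronger readings are tempting and are not supported:
- *That Table 16 tells the programmer to keep only each subject's longest episode.* The note is in two of three rows, and longest PT may mean a choice among preferred terms within a group. The documents do not settle it.
- *That the intervals are too narrow by a known percentage.* Both driving quantities are assumed, and at zero correlation the loss vanishes.
- *That the medians lean toward frequent short events.* This would need recurrent episodes to be shorter, which the documents do not say.

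The three rows also cover different event subsets, so they would not be like for like even under one rule.

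**Conclusion.** The point holds in a limited form. As written, the 95% intervals ignore clustering and are too narrow whenever a subject's episodes are positively correlated. The loss ranges from negligible with few repeats to roughly 89% coverage at a mean of 2 episodes and correlation 0.5, both assumed. Separately, the longest-PT notes are undefined, absent from Appendix H and missing from the all-AESI row, so the three rows do not follow one stated algorithm.

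A different fault in the same appendix comes first. Step 4.b.ii.2 codes a stopped episode as an event only at grade 5 or above and censors it below that. Read literally, resolved episodes are censored and fatal ones count as resolutions. Interval width has no meaning until that is corrected, but correcting it leaves the present point in place.

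The analysis is descriptive. This is a worthwhile clarification, and no efficacy result or error rate depends on it.

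**What to change.** 1. Correct the status coding in Appendix H, step 4.b.ii.2.
2. Keep the episode as the unit, but compute the CI for the median by a subject-level bootstrap (resampling subjects with all their episodes) or a cluster-robust variance. Alternatively, use the first episode per subject and group, parallel to Appendix G.
3. Apply that one rule in all three time-to-resolution rows of Table 16, and delete the longest notes or define them in Appendix H. Do not make the longest episode per subject the default, because it shifts the median upward (step 3 of the working).
4. Report the number of subjects and the number of episodes in each row.
5. Correct the reference in Section 8.5 from Table 15 to Table 16, where these rows are.

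The cost is SAP wording and a small programming change, with no new data. Clustered intervals will be somewhat wider where episodes repeat and are correlated. The first-episode option drops recurrences from the estimate, so the episode counts should then be shown beside it.
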